Cover Letter

Official title: Developing a Down Syndrome Health Instrument

NCT Number: NCT04631237

Document Date: 12/16/2024

Developing a Down Syndrome Health Instrument (DHI)

Original Proposed Statistical Analysis Plan:

Power calculation: Sample sizes are based on several criteria. The basic rule of thumb for psychometric analysis (primarily correlation analyses) is 10 subjects per survey item.⁴⁷ The current conceptual model includes 95 items, with refining in SA1, I plan a final item pool of 70 items. The current target sample sizes will support up to 70 variables (items) available for inclusion in psychometric analyses. For instance, if the final instrument contains 70 items, 700 subjects are sufficient for 80% power to detect a difference of $\geq .25$ standard deviations using type I error of 0.10.

Statistical Analyses: A critical aspect of instrument validation, evaluations include:

Distribution evaluation

Ceiling and floor effects: Item response will be evaluated for ceiling and floor effects. Items that exhibit greater than 85% response in the tail of the distribution within severe respondents will be removed. Comparison will be both between and within sample frames.

Internal Validity

- Reliability: This will include comparison between and within sample frames; retest 2-4 weeks later.
- Internal Consistency: Items that are expected to measure a domain or construct should be related to each other in a systematic way. Internal consistency of item groupings will be evaluated with Cronbach's alpha⁵⁸. Values >0.9 will be interpreted to mean an item is simply being asked over and over again and values <0.4 will be viewed as an unacceptable cut-point relative to item differentiation.
- Test-retest Reliability. To test differences among sample means, Tukey's HSD test with threshold alpha ≤ 0.05 will be used to evaluate all items.⁵⁹

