The primary aim of this research project will be to develop a survey instrument valid to measure health of individuals with Down syndrome ages 0-21 years. As such, the focus is on the psychometric properties of the survey instrument; the study outcomes are the psychometric assessments of the instrument.

Pre-determined Sample Size Calculation and Recruitment Goal

Sample size was determined *a priori* based on the sample size needed to conduct the psychometric analysis. The basic rule of thumb is that (5-10) ten subjects per item are needed for analyses.³⁹ For instance, if the final instrument contains 50 items, 500 subjects are sufficient for 80% power to detect a difference of $\geq .25$ standard deviations using type I error of 0.10. For our DHI with 113 core items, a sample size of 565-1130 caregivers is needed based on using an alpha of .05, a targeted power of .80, and an assumed change of 20% in the score between baseline and follow-up.

Determining “Complete” Surveys

We will closely follow progression through the components of our survey from screening to consent to survey. We considered a survey “Complete” if a participant had a timestamp for completing the DHI section. This occurred when individuals advanced from the final item in the DHI section. Although 683 individuals started the DHI section of our survey, 542 were completed and included in our study.

Item-level Evaluation

Item Distributions (including Missing data)

Ensure no “out of range values” including confirming branching logic followed flow to subsequent questions or skipped as we anticipated / planned.

Basic descriptive statistics are used to report distributions of continuous variables with mean, standard deviation, IQR and frequency for categorical variables. Item distributions evaluated missingness as well as floor and ceiling effects, defined at greater than 85% of responses located in item response anchor. For those with $\geq 85\%$ response at the tails, our research team reviewed the corresponding item and discussed if item should be eliminated. For example, we did not eliminate items related to developmental skills / milestones based on floor and ceiling effects as more than half of individuals are expected to attain some of these skills across the age span studied.

Handling of missing data

Item missingness was evaluated.

Survey-level Evaluation

Scale scoring for all scales/measures:

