1. Develop the scoring algorithm, including minimum number of items requiring response to score. DHI scores are continuous and based on summed means of scale items with higher values indicating better health.
2. Evaluate scale score distributions; evaluate for floor and ceiling effects $\geq 10\%$ response at the tails.

Analysis of Key Psychometric Properties:

1. Factor Structure: principle components (PCA) and principle factor analysis (PFA) methods that included orthogonal (varimax) and oblique rotation (promax).^{39,40} Eigenvalue statistics are used to evaluate the strength of these relationships; a high eigenvalue indicates that an underlying subscale exists and low values indicate that the underlying subscale might not exist. If a subscale's eigenvalue meets the threshold for retention, the next step in the analysis is to evaluate how items relate to a particular factor using factor loading scores. We used standard criteria (eigenvalues > 1) and items within factors (factor loading scores > 0.40)^{39,40} in our iterative scale development process.

2. Internal Validity: Internal dimensional validity of scales was evaluated using factor analysis (FA). Initially, exploratory FA of item grouping within the 3 hypothesized domains (physical, mental, and social health) was conducted to identify factors within each domain, followed by a confirmatory FA of all items within those factors of all domains. The final factor loadings are a result of the confirmatory analysis. Internal consistency was evaluated with Cronbach's alpha. Items with factor loadings < 0.40 were dropped for low convergent validity; items with loadings > 0.9 were reviewed for redundancy and dropped as appropriate.

3. Test-retest Reliability: Reliability analyses included individuals who completed the retest survey. Test-retest reliability of each subscale score was assessed through the interclass correlation coefficient (ICC). An item was used to screen out individuals who experienced major changes in status between the test and the retest. Test-retest reliability was evaluated with paired t-tests and chi square tests at the item level and 2-way mixed-effects intraclass correlation coefficient (ICC) models at the scale level, with a 95% confidence interval of the estimate using the following guideline: poor (< 0.5), moderate ($0.5-0.75$), good ($0.75-0.9$), and excellent (> 0.90).

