Survey-level evaluation	-	Rotation analysis incorporated
Test-retest reliability	Tukey’s HSD test with threshold $\alpha \leq 0.05$ will be used to evaluate all items	Paired t-tests and chi square tests at the item level and 2-way mixed-effects intraclass correlation coefficient (ICC) models at the scale level
External validity	Description of MTMM	Details added on the specific external criterion measures used and analysis method (Pearson correlation)

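### Item-level test-retest reliability is assessed with paired t-tests and chi-square tests, which do not measure agreement, and no item-level agreement coefficient is planned

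*SAP*

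**What the plan says.** The final plan (SAP, Analysis of Key Psychometric Properties, item 3, Test-retest Reliability) splits the analysis by level. For items, "Test-retest reliability was evaluated with paired t-tests and chi square tests at the item level". For scores, it uses "2-way mixed-effects intraclass correlation coefficient (ICC) models at the scale level", with a 95% confidence interval and bands from poor to excellent. Caregivers reporting a major change between test and retest are screened out. The Changes to Statistical Analysis Plan table confirms that this is the final method: "Paired t-tests and chi square tests at the item level and 2-way mixed-effects intraclass correlation coefficient (ICC) models at the scale level". It replaces Tukey's HSD, which appears only in the superseded plan.

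The final plan does not give an alpha for the item tests, a rule for acting on them, the number of retest respondents, or the kind of chi-square test meant. It refers to 113 core items and 542 completed surveys. Neither document plans an item-level agreement coefficient.

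**The concern.** Test-retest reliability asks whether the same respondent, unchanged, gives the same answer on two occasions. That is a question about within-person agreement. A paired t-test compares two means and can be satisfied by answers unrelated from one occasion to the next. It also becomes more sensitive to a trivial shift as the item becomes more repeatable, because the differences then have a smaller SD. A chi-square test on the test-by-retest table asks only whether the answers are associated. A chi-square test on the two sets of margins asks only whether the distributions match.

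The SAP says the study outcomes are the psychometric assessments of the instrument, so the item-level retest results are part of what will be reported. At stake is whether they can tell a reader which of the retained items are unstable.

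**Working it through.** The plan gives no figure for this analysis, so there is none to reproduce. The check asks how each test behaves for items of known reliability.

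**Inputs.** From the SAP: the tests named, and 542 completed surveys as a ceiling on the retest n. Assumed, because the documents do not say: two-sided alpha 0.05, retest n of 50, 100 or 200, and the values of correlation r, shift d (in SD units) and kappa.

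**Paired t-test, no shift.** If both occasions have the same mean, the null hypothesis is true whatever r is. An item with r = 0 is therefore non-significant about 95% of the time at any n. Simulated 5-level items gave 95% to 96% at n from 50 to 542.

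**Paired t-test, small shift.** The SD of the differences is √(2(1 − r)), so the noncentrality is d√n / √(2(1 − r)). With d = 0.1:

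- r = 0.9: 0.1/√0.2 = 0.2236, times √n
- r = 0: 0.1/√2 = 0.0707, times √n

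| n | Noncentrality, r = 0.9 | P(significant), r = 0.9 | Noncentrality, r = 0 | P(significant), r = 0 |
|---|---|---|---|---|
| 50 | 1.58 | 34% | 0.50 | 8% |
| 100 | 2.24 | 60% | 0.71 | 11% |
| 200 | 3.16 | 88% | 1.00 | 17% |
| 542 (ceiling) | 5.21 | >99% | 1.65 | 38% |

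The absolute-agreement ICC of the first item is about r/(1 + d²/2) = 0.9/1.005 = 0.896; that of the second is 0. At every n the test flags the reliable item more often than the worthless one.

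**Chi-square, if it tests association.** For a binary item with equal margins, phi equals kappa and the noncentrality on 1 df is n × kappa². With kappa = 0.25 this is 3.125, 6.25 and 12.5 at n = 50, 100 and 200, so the test is significant 42%, 71% and 94% of the time. In the extreme, 100 respondents who all reverse their answer (50 each way) give a continuity-corrected chi-square of 96.0, p about 1e-22, with kappa = −1.

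**Chi-square, if it compares margins.** In the simulation, items with r = 0 and equal margins were non-significant about 94% to 96% of the time. This form, too, is silent on agreement.

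**Agreement coefficient on the same simulated items.** The item ICC was about 0.00 with no reliability, 0.27 for a weak item (latent r = 0.3), and 0.88 to 0.90 for a reliable item (latent r = 0.95) with or without a small shift, at every n from 50 to 542. It separates the cases that the planned tests do not.

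**The case against.** A reader might infer that unreliable items are being kept and reliable ones discarded. The documents do not support that. No item is retained or dropped on its retest result. The stated item decisions rest on loadings (below 0.40 dropped, above 0.9 reviewed) and on review of items with 85% or more of responses at the tails. An alpha of 0.05 for this analysis appears only in the superseded Tukey plan. Multiplying 113 items by 0.05 to predict false flags therefore presumes a threshold, and a test size, that the final plan does not state.

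Three further points have weight:

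- The scores users will rely on are assessed by an ICC with a 95% CI. The SAP does not say whether this is the absolute-agreement or the consistency form. That is missing detail, and it does not show that a systematic shift is ignored.
- An item answered at random would be expected to load below 0.40 and be dropped, so most pure-noise items should go by another route.
- The chi-square may be a paired form such as McNemar or Bowker, which is a legitimate check for shift. The association figures above would then not apply.

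The retest n is also unknown, and a significant t-test for a reliable item needs a real small shift or a chance rejection.

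What stands after this is narrower but firm. On no reading does either test quantify agreement. Loadings and Cronbach's alpha describe a single occasion. A subscale ICC does not show which of its items are unstable.

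**Conclusion.** The concern holds at the item level only. The planned item tests do not measure test-retest reliability, and no other planned analysis fills that gap for the items that survive the loading rule. The t-test's pass rate of about 95% for an item with zero correlation and no shift does not depend on n. Its higher flag rate for the reliable item with a 0.1 SD shift (34%, 60% and 88% against 8%, 11% and 17%) holds at every n examined, though its size depends on the assumed n, alpha and shift. The chi-square rates of 42%, 71% and 94% at kappa 0.25 apply only if association is what is tested.

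Subscale reliability and the stated item-retention decisions are not affected. This should be fixed, but it does not undermine the scale-level reliability assessment.

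**What to change.** Make the item-level reliability statistic an agreement coefficient: kappa for binary or nominal items, weighted kappa for ordinal items, and absolute-agreement ICC for continuous items. Give each with a 95% CI and the number of retest respondents contributing. Keep the paired t-test, or a McNemar or Bowker test, only as a secondary check for systematic shift, and say which chi-square test is meant. While editing the section, name the form of the scale-level ICC.

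The cost is a few sentences in the SAP and a little more analysis on data already collected. The one drawback is that kappa can be low for items with very skewed responses even when most answers match, so percent agreement should be reported beside it.
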